Appendix E: International Myeloma Working Group Uniform Response Criteria

Response Category	Definition

sCR Stringent Complete Response
	
CR criteria as defined below AND
 
 • Normal free light chain (FLC) ratio 
AND
 
 • Absence of phenotypically aberrant PCs in bone marrow^b analyzed by multiparametric flow cytometry

CR Complete Response
	
 • Negative immunofixation on the serum and urine 
AND
 
 • Disappearance of any soft tissue plasmacytoma(s) 
AND
 
 • $\leq 5\%$ plasma cells in bone marrow^b. • In case the only measurable disease in a patient with CR at baseline is the serum FLC level, a normal FLC ratio of 0.26 to 1.65 is required additionally to qualify for CR.

VGPR Very Good Partial Response
	
 • Serum and urine M-protein detectable by immunofixation but not by electrophoresis (PEP) or $\geq 90\%$ reduction from baseline serum) AND urine M-protein level < 100 mg/ 24h 
AND
 
 • In case of presence of soft tissue plasmacytoma(s) at baseline, disappearance of any soft tissue plasmacytomas 
In case the only measurable disease in a patient with VGPR at baseline is the serum FLC level (i.e. no measurable disease in serum and urine PEP), a decrease of $> 90\%$ in the difference between involved and uninvolved FLC levels from baseline is required.

PR Partial Response
	
$\geq 50\%$ reduction from baseline in serum M-protein
 
AND
 
$\geq 90\%$ reduction from baseline in 24h urinary M-protein OR urine M-protein < 200 mg/24h
 
If serum and urine M-protein are non-measurable at baseline, a $\geq 50\%$ reduction from baseline in the difference between involved and uninvolved FLC levels is required in place of the M-protein criteria.
 
If serum and urine M-protein are non-measurable, and serum free light assay is also non-measurable, $\geq 50\%$ reduction from baseline in percent plasma cells in bone marrow is required instead of M-protein measurement, provided baseline plasma cells in bone marrow was $\geq 30\%$.
 
AND
 
In case of presence of soft tissue plasmacytoma(s) at baseline, a reduction in the SPD by $\geq 50\%$ is required.

CONFIDENTIAL

STUDY DRUG: MLN9708
FINAL PROTOCOL: 11 APRIL 2014
AMENDMENT NUMBER 3: 11 FEBRUARY 2016

SCRI INNOVATIONS STUDY NUMBER: MM 42

VERSION 4

Appendix E: International Myeloma Working Group Uniform Response Criteria: Complete Response and Other Response Categories (continuation)

SD	Not meeting criteria for sCR, CR, VGPR, PR or PD
PD Progressive Disease	
Increase of $\geq 25\%$ from the nadir in at least one of the following criteria:
 
 • serum M-protein (absolute increase must be ≥ 0.5 g/dL and absolute value must be ≥ 1 g/dL) • urine M-protein (absolute increase must be ≥ 200 mg/24h) • only in patients with non-measurable serum and urine M-protein levels: difference in involved and uninvolved FLC levels (absolute increase must be >10 mg/L) • Bone marrow plasma cell percentage (absolute % must be $\geq 10\%$) 
OR
 
 • development of new lytic bone lesions or increase from baseline in size of lytic bone lesion(s) 
OR
 
 • development of new soft tissue plasmacytoma(s) or definite increase from nadir in existing soft tissue plasmacytomas 
OR
 
 • development of hypercalcemia (corrected serum calcium >11.5 mg/dL) for patients without hypercalcemia at baseline. In case of preexisting hypercalcemia at baseline, PD will only be assessed due to the hypercalcemia criterion in case the corrected serum calcium level was ≤ 11.5 mg/dL post-baseline and increased thereafter beyond 11.5 mg/dL.

^aAll response categories require two consecutive assessments made at any time before the institution of any new therapy; all categories also require no known evidence of progressive or new bone lesions if radiographic studies were performed. Radiographic studies are not required to satisfy these response requirements.

^bConfirmation with repeat bone marrow biopsy not needed.

Source: Kyle RA and Rajkumar SV Criteria for diagnosis, staging, risk stratification and response assessment of multiple myeloma. Leukemia 2009. 23:3-9

CONFIDENTIAL

SCRI INNOVATIONS STUDY NUMBER: MM 42

STUDY DRUG: MLN9708

FINAL PROTOCOL: 11 APRIL 2014

AMENDMENT NUMBER 3: 11 FEBRUARY 2016

VERSION 4

Appendix F: National Institutes of Health Consensus Development Project on Criteria for Clinical Trials in Acute and Chronic Graft-Versus-Host Disease

Organ Staging of Acute GVHD

Stage	Skin	Liver	GI tract
Organ staging 0	No rash due to GvHD	Bilirubin < 2 mg/dl or 35 µmol/l	None
I	Maculopapular rash < 25% of body surface area without associated symptoms	Bilirubin from 2 mg/dl to < 3 mg/dl or 35-50 µmol/l	Diarrhea > 500-1000 ml/day; nausea and emesis
II	Maculopapular rash or erythema with puritis or other associated symptoms ≥ 25% of body surface area or localized desquamation	Bilirubin from 3 mg/dl to < 6 mg/dl or 51-102 µmol/l	Diarrhea > 1000 to 1500 ml/day; nausea and emesis
III	Generalized erythroderma or symptomatic macular, papular, or vesicular eruption with bullous formation or desquamation covering ≥ 50% of body surface area	Bilirubin 6 mg/dl to < 15 mg/dl or 103-225 µmol/l	Diarrhea > 1500 ml/day; nausea and emesis
IV	Generalized exfoliative dermatitis or bullous eruption	Bilirubin > 15 mg/dl or > 225 µmol/l	Diarrhea > 1500 ml/day; nausea and emesis. Abdominal pain or ileus

Overall Clinical Grading of Acute GVHD

Grade	Skin	Liver	GI tract	Performance status
0	0	0	0	0
I	1-2	0	0	0
II	1-3	1	1	1
III	2-3	2-3	2-3	2
IV	2-4	2-4	2-4	2-4

Reference for both tables for acute GVHD: Przepiorka et al. 1995

CONFIDENTIAL

STUDY DRUG: MLN9708

SCRI INNOVATIONS STUDY NUMBER: MM 42

FINAL PROTOCOL: 11 APRIL 2014

AMENDMENT NUMBER 3: 11 FEBRUARY 2016

VERSION 4

Organ Staging of Chronic GVHD

	SCORE 0	SCORE 1	SCORE 2	SCORE 3
PERFORMANCE SCORE:  KPS ECOG LPS	 Asymptomatic and fully active (ECOG 0; KPS or LPS 100%)	 Symptomatic, fully ambulatory, restricted only in physically strenuous activity (ECOG 1, KPS or LPS 80-90%)	 Symptomatic, ambulatory, capable of self-care, >50% of waking hours out of bed (ECOG 2, KPS or LPS 60-70%)	 Symptomatic, limited self-care, >50% of waking hours in bed (ECOG 3-4, KPS or LPS <60%)
SKIN Clinical features:  Maculopapular rash  Lichen planus-like features  Papulosquamous lesions or ichthyosis  Hyperpigmentation  Hypopigmentation  Keratosis pilaris  Erythema  Erythroderma  Poikiloderma  Sclerotic features  Pruritus  Hair involvement  Nail involvement % BSA involved 	 No Symptoms	 <18% BSA with disease signs but NO sclerotic features	 19-50% BSA OR involvement with superficial sclerotic features "not hidebound" (able to pinch)	 >50% BSA OR deep sclerotic features "hidebound" (unable to pinch) OR impaired mobility, ulceration or severe pruritus
MOUTH	 No symptoms	 Mild symptoms with disease signs but not limiting oral intake significantly	 Moderate symptoms with disease signs with partial limitation of oral intake	 Severe symptoms with disease signs on examination with major limitation of oral intake
EYES Mean tear test (mm):  >10  6-10  ≤5  Not done	 No symptoms	 Mild dry eye symptoms not affecting ADL (requiring eyedrops ≤ 3 x per day) OR asymptomatic signs of keratoconjunctivitis sicca	 Moderate dry eye symptoms partially affecting ADL (requiring drops > 3 x per day or punctal plugs), WITHOUT vision impairment	 Severe dry eye symptoms significantly affecting ADL (special eyewear to relieve pain) OR unable to work because of ocular symptoms OR loss of vision caused by keratoconjunctivitis sicca
GI TRACT	 No symptoms	 Symptoms such as dysphagia, anorexia, nausea, vomiting, abdominal pain or diarrhea without significant weight loss (<5%)	 Symptoms associated with mild to moderate weight loss (5-15%)	 Symptoms associated with significant weight loss >15%, requires nutritional supplement for most calorie needs OR esophageal dilation
LIVER	 Normal LFT	 Elevated Bilirubin, AP*, AST or ALT <2 x ULN	 Bilirubin >3 mg/dl or Bilirubin, enzymes 2-5 x ULN	 Bilirubin or enzymes > 5 x ULN

CONFIDENTIAL

SCRI INNOVATIONS STUDY NUMBER: MM 42

STUDY DRUG: MLN9708
 FINAL PROTOCOL: 11 APRIL 2014
 AMENDMENT NUMBER 3: 11 FEBRUARY 2016

VERSION 4

	SCORE 0	SCORE 1	SCORE 2	SCORE 3
LUNGS [†]	 No symptoms	 Mild symptoms (shortness of breath after climbing one flight of steps)	 Moderate symptoms (shortness of breath after walking on flat ground)	 Severe symptoms (shortness of breath at rest; requiring O ₂)
FEV1 				
DLCO 	 FEV1 > 80% OR LFS=2	 FEV1 60-79% OR LFS 3-5	 FEV1 40-59% OR LFS 6-9	 FEV1 ≤39% OR LFS 10-12
JOINTS AND FASCIA	 No symptoms	 Mild tightness of arms or legs, normal or mild decreased range of motion (ROM) AND not affecting ADL	 Tightness of arms or legs OR joint contractures, erythema thought due to fasciitis, moderate decrease ROM AND mild to moderate limitation of ADL	 Contractures WITH significant decrease of ROM AND significant limitation of ADL (unable to tie shoes, button shirts, dress self etc.)
GENITAL TRACT	 No symptoms	 Symptomatic with mild signs on exam AND no effect on coitus and minimal discomfort with gynecologic exam	 Symptomatic with moderate signs on exam AND with mild dyspareunia or discomfort with gynecologic exam	 Symptomatic WITH advanced signs (stricture, labial agglutination or severe ulceration) AND severe pain with coitus or inability to insert vaginal speculum

Other indicators, clinical manifestations or complications related to chronic GVHD (check all that apply and assign a score to its severity (0-3) based on its functional impact where applicable (none – 0, mild -1, moderate -2, severe – 3)

Esophageal stricture or web ___ Pericardial Effusion ___ Pleural Effusion(s) ___
Ascites (serositis) ___ Nephrotic syndrome ___ Peripheral Neuropathy ___
M yasthenia Gravis ___ Cardiomyopathy ___ Eosinophilia > 500/μl ___
Polymyositis ___ Cardiac conduction defects ___ Coronary artery involvement ___
Platelets <100,000/μl ___ Progressive onset ___

OTHERS: Specify: _____

Reference for chronic GVHD tables: Filipovich et al. 2005

Appendix G: Pregnancy Reporting Form

Pregnancy Form

Report Type: Initial Follow-up Date of Report: ___/___/___
DD MM Yr

REPORTER INFORMATION: (Please forward if an alternative physician is more appropriate)

Reporter name: _____ Title: _____

Address: _____ Telephone No.: _____ Fax No. _____

City, State/Province: _____ Postal Code: _____ Country: _____

FATHER'S INFORMATION Father Unknown

Initials: _____ Date of Birth: ___/___/___ or Age: _____ years
DD MM Yr

Participating in an MPI clinical study? No Yes
If no, what company product was taken: _____
If yes, please provide: Study drug: _____ Protocol No: _____
 Center No: _____ Patient No: _____

Medical / Familial / Social History
 (I.e. Include chronic illnesses: specify, familial birth defects/genetic/chromosomal disorders; habitual exposure: specify, alcohol/tobacco; drug exposure: specify, substance abuse and medication use. Please include drug treatment prior to or around the time of conception and/or during pregnancy)

Race: _____
 Occupation: _____
 Number of children: _____

MOTHER'S INFORMATION:

Initials: _____ Date of Birth: ___/___/___ or Age: _____ years
DD MM Yr

Participating in an MPI clinical study? No Yes
If no, what company product was taken: _____
If yes, please provide: Study drug: _____ Protocol No: _____
 Center No: _____ Patient No: _____

Medical / Familial / Social History
 (I.e. Include alcohol/tobacco and substance abuse; complications of past pregnancy, labor/delivery, fetus/baby; illnesses during this pregnancy; assisted conception: specify; other disorders including familial birth defects/genetic/chromosomal disorders; method of diagnosis consanguinity, etc.)

Number of previous pregnancies: Full term ____ Pre-term ____
 Outcomes of previous pregnancies:
 (Please indicate number of occurrences)

- Spontaneous abortion: _____
- Therapeutic abortion: _____
- Elective abortion: _____
- Other: _____
- Normal live birth: _____
- Children born with defects: _____
- Stillbirth: _____
- Outcome unknown: _____

MOTHER'S DRUG EXPOSURE INFORMATION
 Please include medical prescriptions, vaccinations, medical devices, OTC products, pregnancy supplements (such as folic acid, multivitamins)

Product Name	Dosage	Route administered to patient	Date of first use (DD/MM/Yr)	Date of end treatment (DD/MM/Yr)	Indication	Contraindicated to pregnancy
			(/ /)	(/ /)		 Yes  No  Unk
			(/ /)	(/ /)		 Yes  No  Unk
			(/ /)	(/ /)		 Yes  No  Unk
			(/ /)	(/ /)		 Yes  No  Unk

e-Pregnancy Form (27 November 2013)

CONFIDENTIAL
 SCRI INNOVATIONS STUDY NUMBER: MM 42

STUDY DRUG: MLN9708
 FINAL PROTOCOL: 11 APRIL 2014
 AMENDMENT NUMBER 3: 11 FEBRUARY 2016

VERSION 4

Appendix G: Pregnancy Reporting

Pregnancy Form

CURRENT PREGNANCY INFORMATION	
Period at exposure: _____ weeks Trimester  1  2  3 Date of last menstrual period: ____/____/____  Unknown <small style="margin-left: 100px;">DD MM Yr</small>	Fetal/Neonatal Status  Normal  Birth defect (structural/chromosomal disorder)*  Other (non-structural, premature birth, intrauterine death/stillbirth)* <small>*If box is checked, please note details in "Additional details" section below</small>
Pregnancy Status  Pregnancy Ongoing Estimated date of delivery: ____/____/____ <small style="margin-left: 100px;">DD MM Yr</small>  Live Birth  Stillbirth  Early Termination  Spontaneous abortion*  Therapeutic abortion*  Elective abortion*  Other*: _____ <small>*If box is checked, please note reason in "Additional Details" section below</small>	Additional Details: Is there evidence of a defect from a prenatal test?  Yes  No If yes, indicate which test(s) showed evidence of birth defect:  Ultrasound  Amniocentesis  Maternal Serum-Alpha-Fetoprotein  Chorionic Villi Sampling  Human Chorionic Gonadotropin  Other: _____ Please specify details of defect(s), disorder(s), and/or other anomaly(ies): _____ _____ What are the defect(s) attributed to: _____
Infant Information: Gestational weeks at birth or at termination: _____ weeks Date of birth or termination: ____/____/____ <small style="margin-left: 100px;">DD MM Yr</small> If multiple births (e.g. twins), indicate number: _____ (Please complete separate form for each child) Birth Order (1, 2, 3, etc.) _____ Breast-fed:  Yes  No  Unk Method of delivery:  Normal vaginal  Caesarean section  Other: _____	Sex:  Male  Female  Unk Length: ____  cm  in Weight: ____  g  lbs Head circumference: ____  cm  in Apgar score (0-10) at 1 minute: ____  Unk Apgar score (0-10) at 5 minute: ____  Unk Resuscitation required:  Yes  No  Unk Admission to intensive care required:  Yes  No  Unk
Additional Notes: _____ _____ _____	

Please attach RELEVANT LABORATORY TESTS AND PROCEDURES (e.g. results of ultrasounds, amniocentesis, chorionic villi sampling, or miscellaneous testing as applicable). In the case of an abnormal evolution or outcome, please send copies of results of all relevant laboratory testing and procedures, including pathology results of products of conception and or autopsy reports if applicable. Please submit any additional relevant information on a separate sheet.

Investigator signature: _____	Date: ____/____/____ <small style="margin-left: 100px;">DD MM Yr</small>
Investigator Name: _____	

Form

1.1 Objectives	
Primary Objective:	Safety of MLN9708 when used as maintenance after allogeneic stem cell transplant for multiple myeloma
Secondary Objectives:	
Maximum-tolerated dose (MTD) of MLN9708 in this patient population
 
Progression-free survival (PFS) at 2 years after initiation of maintenance therapy
 
Overall survival (OS) at 2 years after allogeneic stem cell transplant
 
Incidence of graft-versus-host disease (GVHD) in patients receiving allogeneic stem cell transplant and maintenance with MLN9708
 
Effect of MLN9708 on immune effector cells after allogeneic stem cell transplant

1.2 Study Design	
Study Type	 Non-Randomized  Randomized (Allocation Ratio:)
Details	
This is a Phase II, open-label, multicenter, non-randomized study to determine the feasibility of MLN9708 as maintenance after allogeneic stem cell transplant for multiple myeloma. Patients will be enrolled between Days 45 and 120 after allogeneic transplant and will receive MLN9708 on Days 1, 8, and 15 of each 28-day cycle for 6 cycles. Up to 18 patients will be enrolled in the dose-escalation phase to define the MTD of MLN9708. An additional 20 patients will be enrolled in the expansion phase at the MTD.
 
PFS is defined as the time from the first day of study drug administration (Day 1) to disease progression as defined by the International Myeloma Working Group Uniform Response Criteria (see Appendix E of protocol), or death on study. Patients who are alive and free from disease progression will be censored at the date of last tumor assessment.
 
OS is defined as the time from the first day of study drug administration (Day 1) to death on study. Patients who are alive will be censored at the date of last known date alive.
 
PFS and OS (efficacy secondary endpoints) estimates will be generated using Kaplan-Meier methods, both for all patients enrolled and those patients receiving the MTD. Two-year PFS and OS estimates with 95% confidence intervals (CIs), and median PFS and OS with 95% CIs, will be generated and reported accordingly.

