3. STUDY PATIENT POPULATION AND DISCONTINUATION

3.1 Inclusion Criteria

Patients must meet the following criteria in order to be included in the research study:

1. Symptomatic multiple myeloma or asymptomatic myeloma with myeloma-related organ damage diagnosed according to standard criteria in patients who received allogeneic transplant due to high-risk prognostic features, such as, but not limited to:
 - Chromosome 17p, partial deletion (del(17p), t(4;14), t(14;16), t(14;20)
 - Plasma cell leukemia
 - Progression-free survival of less than 2 years after autologous stem cell transplant

CONFIDENTIAL

STUDY DRUG: MLN9708
FINAL PROTOCOL: 11 APRIL 2014
AMENDMENT NUMBER 3: 11 FEBRUARY 2016

SCRI INNOVATIONS STUDY NUMBER: MM 42

VERSION 4

2. Evidence of engraftment of neutrophils (absolute neutrophil count [ANC] >1000 cells/mm³) and platelets (platelets >60,000 cells/mm³ [dose escalation phase] and >50,000 cells/mm³ [dose expansion phase])
3. Achievement of at least a PR prior to allogeneic stem cell transplant.
4. Adequate liver function defined as:
 - Alanine aminotransferase (ALT) and aspartate aminotransferase (AST) ≤3.0 x the upper limit of normal (ULN)
 - Total bilirubin ≤2.0 x ULN
5. Adequate renal function defined as creatinine clearance ≥30 mL/min, estimated or calculated.
6. Aged ≥18 and ≤70 years, at time of enrollment
7. Ability to swallow oral medication
8. Absence of gastrointestinal symptoms that precludes oral intake and absorption of MLN9708 (nausea, vomiting, diarrhea, malabsorption)
9. Off antibiotics and amphotericin B formulations, voriconazole or other anti-fungal therapy for the treatment of proven, probable or possible infections (defined in accordance with the European Organization for Research and Treatment of Cancer/Invasive Fungal Infections Cooperative Group and the National Institute of Allergy and Infectious Diseases Mycoses Study Group [EORTC/MSG] criteria)
10. Eastern Cooperative Oncology Group (ECOG) Performance Status score of ≤ 2 (Appendix A)
11. Life expectancy ≥3 months
12. Male patients with female partners of childbearing potential and female patients of childbearing potential are required to use two forms of **acceptable** contraception, including one barrier method, during their participation in the study and for 90 days following last dose of study drug. Male patients must also refrain from donating sperm during their participation in the study (Appendix C).

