16. Systemic treatment with strong inhibitors of cytochrome P450 (CYP) 1A2 (CYP1A2) (fluvoxamine, enoxacin, ciprofloxacin), moderate inhibitors of CYP1A2 (mexiletine, propafenone, and zileuton), strong inhibitors of CYP3A (clarithromycin, telithromycin, itraconazole, voriconazole, ketoconazole, posaconazole, and nefazodone), moderate CYP3A inhibitors (amprenavir, aprepitant, diltiazem, erythromycin, fosamprenavir, grapefruit-containing products including grapefruit juice, and verapamil), or clinically significant CYP3A inducers (rifampin, rifapentine, rifabutin, carbamazepine, oxcarbazepine, primidone, phenytoin, phenobarbital), or use of Ginkgo biloba or St. John's wort within 14 days before study drug administration in the study.
17. Presence of other active cancers or history of treatment for invasive cancer \leq 5 years. Patients with Stage I cancer who have received definitive local treatment and are considered unlikely to recur are eligible. All patients with previously treated in situ

CONFIDENTIAL

STUDY DRUG: MLN9708
 FINAL PROTOCOL: 11 APRIL 2014
 AMENDMENT NUMBER 3: 11 FEBRUARY 2016

SCRI INNOVATIONS STUDY NUMBER: MM 42

VERSION 4

carcinoma (i.e., non-invasive) are eligible, as are patients with history of non-melanoma skin cancer.

18. Psychological, familial, sociological, or geographical conditions that do not permit compliance with the protocol.
19. Graft versus host disease > Grade 2; or GVHD Grade 1 or Grade 2 which requires > 0.5 mg/kg methylprednisolone, or equivalent

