5. STUDY DESIGN

This is a Phase II, open-label, multicenter, non-randomized study to determine the feasibility of MLN9708 as maintenance after allogeneic stem cell transplant for multiple myeloma. Patients will be enrolled between Days 45 and 120 after allogeneic transplant and will receive MLN9708 on Days 1, 8, and 15 of each 28-day cycle for 6 cycles. Up to 18 patients will be enrolled in the dose-escalation phase to define the MTD of MLN9708. An additional 20 patients will be enrolled in the expansion phase at the MTD.

Up to 5 study sites are planned in the United States.

Dosing will start at 2.3 mg. If acceptable tolerability is demonstrated, escalations will be made to 3 mg and to the maximum-planned dose (MPD) of 4 mg. Once the MTD/MPD is determined, enrollment into the expansion phase will proceed at that dose. The study schema is presented in Figure 1.

[figure not shown]
CONFIDENTIAL

STUDY DRUG: MLN9708
FINAL PROTOCOL: 11 APRIL 2014
AMENDMENT NUMBER 3: 11 FEBRUARY 2016

SCRI INNOVATIONS STUDY NUMBER: MM 42

VERSION 4

Figure 1 Study Schema

MTD = Maximum-tolerated dose
MPD = Maximum-planned dose

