7.2 Baseline Study Assessments

The following information will be collected and procedures will be performed for each patient at Baseline ≤ 7 days prior to initiation of treatment unless otherwise noted:

- Written informed consent prior to any other study-related procedures (≤ 28 days of first study drug treatment)
- Medical history including:
 - Review of systems
 - Prior treatments for all significant conditions, including neuropathy
 - ECOG performance status prior to conditioning for allogeneic transplant
 - Pre allogeneic transplant overall comorbidity index
 - Transplant history including
 - Conditioning regimens including total dose and start and end dates
 - Type of transplant (syngeneic, autologous or allogeneic; bone marrow versus peripheral blood stem cells; match related versus matched unrelated)
 - Date of transplant
 - Date of engraftment of white cells and platelets
 - Number of allogeneic CD34+ cells received (record for allogeneic transplant only)
 - Graft versus host disease prophylaxis
 - Post-transplant infections
 - Prior systemic therapy for multiple myeloma with start and end dates and best overall response to therapy
 - Prior radiation therapy for multiple myeloma with total dose, start and end dates
 - Prior surgeries for multiple myeloma and date
- Physical examination, including a neurological evaluation, measurements of height (first visit), weight, and vital signs (resting heart rate, blood pressure [BP], respiratory rate, and oral temperature)
- ECOG performance status (see Appendix A)
- Acute GVHD assessment with overall grade (see Appendix F)
- Chronic GVHD assessment with overall grade (see Appendix F)
- 12-lead ECGs in triplicate approximately 5 minutes apart

CONFIDENTIAL

STUDY DRUG: MLN9708

SCRI INNOVATIONS STUDY NUMBER: MM 42

FINAL PROTOCOL: 11 APRIL 2014

AMENDMENT NUMBER 3: 11 FEBRUARY 2016

VERSION 4

- Chest X-ray
- Concomitant medication review of all medications taken within 21 days of first planned study drug administration for conditions other than GVHD
- Concomitant medication review specifically for GVHD prophylaxis since receiving the allogeneic transplant
- CBC, including 3-part differential (total neutrophil count including bands, lymphocytes, monocytes) hemoglobin, hematocrit, and platelets

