10.4.2 Efficacy Analysis

- PFS, defined as the time from the first day of study drug administration (Day 1) to disease progression as defined by the International Myeloma Working Group Uniform Response Criteria (see Appendix E), or death on study. Patients who are alive and free from disease progression will be censored at the date of last tumor assessment.
- OS, defined as the time from the first day of study drug administration (Day 1) or death on study. Patients who are alive will be censored at the date of last known date alive.

Progression-free survival and OS (efficacy secondary endpoints) estimates will be generated using Kaplan-Meier methods, both for all patients enrolled and those patients receiving the MTD. Two-year PFS and OS estimates with 95% confidence intervals (CIs), and median PFS and OS with 95% CIs, will be generated and reported accordingly.

The effect of MLN9708 on immune effector cells after allogeneic stem cell transplant will be analyzed by examining the difference in the actual change from baseline at Cycle 1 Day 4, Cycle 1 Day 8, Cycle 1 Day 15, and Cycle 2 Day 1, and the percentage change from baseline at Cycle 1 Day 4, Cycle 1 Day 8, Cycle 1 Day 15, and Cycle 2 Day 1, among those patients participating in the biomarker research component. Each analysis will be performed within dose level and total patients.

The following parameters will be examined:

- CD3+, CD4+, CD8+, CD45+, CD19+ and CD56+/CD16+ cell counts, by fluorescence-activated cell sorting
- Regulatory T cell counts by intracellular staining of FoxP3, and surface staining of CD4+ and CD25+ cells
- Inflammatory cytokine concentrations of IL-1 β , IL-6, IL-8, IL-10 and TNF- α .

CONFIDENTIAL

STUDY DRUG: MLN9708

SCRI INNOVATIONS STUDY NUMBER: MM 42

FINAL PROTOCOL: 11 APRIL 2014

AMENDMENT NUMBER 3: 11 FEBRUARY 2016

VERSION 4

For each parameter, the actual change from baseline and the percentage change from baseline, at each time point, will be analyzed using the two-sided Wilcoxon signed-rank procedure to test whether either the change is statistically different from zero.

The significance level will be set at 10%, and there will be no adjustment to the alpha level for multiple comparisons. The rationale for the reporting of p-values in these analyses is for hypothesis-generating purposes only.

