Definition of Endpoints:	Start Date:  Date of Randomization  Date of First Treatment End Date (specify for all pertinent endpoints): Progression-Free Survival: Event = Progression or Death 
  
 Situation	Date of Event or Censoring	Outcome	
   
 No baseline assessment	Date of first treatment	Censored	
 
 PD documented between scheduled visits, did not die, and received no subsequent therapy	First date of evaluated overall response = PD	Event	
 
 PD documented between scheduled visits, did not die, but received subsequent therapy prior to incurring progression event	Date of last evaluable tumor assessment prior to start of subsequent therapy	Censored	
 
 Death while on-study without previous PD, and received no subsequent therapy	Date of death	Event	
 
 Death while on-study and had previous PD, and received no subsequent therapy	First date of evaluated overall response = PD	Event	
  
	Situation	Date of Event or Censoring	Outcome	No baseline assessment	Date of first treatment	Censored	PD documented between scheduled visits, did not die, and received no subsequent therapy	First date of evaluated overall response = PD	Event	PD documented between scheduled visits, did not die, but received subsequent therapy prior to incurring progression event	Date of last evaluable tumor assessment prior to start of subsequent therapy	Censored	Death while on-study without previous PD, and received no subsequent therapy	Date of death	Event	Death while on-study and had previous PD, and received no subsequent therapy	First date of evaluated overall response = PD	Event
Situation	Date of Event or Censoring	Outcome																	
No baseline assessment	Date of first treatment	Censored																	
PD documented between scheduled visits, did not die, and received no subsequent therapy	First date of evaluated overall response = PD	Event																	
PD documented between scheduled visits, did not die, but received subsequent therapy prior to incurring progression event	Date of last evaluable tumor assessment prior to start of subsequent therapy	Censored																	

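### The OS objective is survival 2 years after transplant, but OS is measured from first dose in patients who enrol 45–120 days after transplant, so the stated objective is not estimated

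*SAP*

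**What the plan says.** **Objective.** SAP 1.1 lists, as a secondary objective, "Overall survival (OS) at 2 years after allogeneic stem cell transplant". The Protocol Synopsis and Protocol 2.2 set the same objective. Time zero is the transplant.

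**Definition.** SAP 1.2 says "OS is defined as the time from the first day of study drug administration (Day 1) to death on study". Protocol 10.4.2 reads "OS, defined as the time from the first day of study drug administration (Day 1) or death on study", where *or* is evidently a slip for *to*. In the SAP's efficacy section (5/6, Definition of Endpoints) the ticked start date is "Date of First Treatment", one box serving both PFS and OS. Time zero is the first dose.

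**Gap between the two.** Protocol section 5 says "Patients will be enrolled between Days 45 and 120 after allogeneic transplant", and SAP 1.2 repeats it.

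**Planned output.** Protocol 10.4.2 and SAP 1.2 plan Kaplan-Meier estimates of 2-year and median OS with 95% CIs; the SAP table and figure list adds one OS table and one OS curve. No estimate from transplant, no conversion between clocks and no delayed entry is planned.

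**Comparison with PFS.** The PFS objective names the start of maintenance as its origin, which agrees with its Day 1 definition. The mismatch affects OS only.

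**The concern.** Every patient has already lived 45 days or more after transplant when the OS clock starts, so the two origins differ for everyone and by an amount that varies between patients. A 2-year Kaplan-Meier estimate on the Day 1 clock therefore cannot be read as survival 2 years after transplant.

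If the planned figure is reported against the objective as worded, a reader who sets it beside other post-transplant results will be comparing different time points. The direction is predictable: the Day 1 figure is lower than survival at 24 months after transplant in the same patients. The confidence interval gives no warning, because it describes sampling error and not a wrong label.

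Conditioning matters as well. Entry requires "Evidence of engraftment of neutrophils" and of platelets, and patients with "Graft versus host disease > Grade 2" are excluded. Any post-transplant survival figure from this trial describes patients who lived and recovered well enough to enrol, and must say so.

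**Working it through.** The documents state no OS rate, power or event count for OS, so there is no OS figure to reproduce. The only related count is the sample size: 3 cohorts × 6 = 18, and 18 + 20 = 38, as stated.

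**Inputs from the documents**
- Gap from transplant to enrolment: 45 to 120 days (Protocol 5, SAP 1.2); midpoint 82.5 days.
- Landmark: 2 years = 730.5 days.
- Maximum n: 38 (Protocol Synopsis).

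**Assumptions (not in the documents)**
- First dose on the day of enrolment.
- Constant hazard.
- 2-year OS from Day 1, S, of 50%, 60% or 70%.

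**Step 1: where the landmarks fall.** One month = 30.4375 days.
- Planned 2-year OS, in days after transplant: 730.5 + 45 = 775.5 (25.5 months) to 730.5 + 120 = 850.5 (27.9 months).
- Stated objective, in days after first dose: 730.5 − 45 = 685.5 (22.5 months) to 730.5 − 120 = 610.5 (20.1 months).

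**Step 2: size of the shift.** Let m be the gap in months (1.48, 2.71 and 3.94). Survival at 24 months after transplant, given alive at first dose, is S^((24 − m)/24).

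| S at 2 years from Day 1 | Gap 45 d | Gap 82.5 d | Gap 120 d |
|---|---|---|---|
| 0.50 | 0.522 | 0.541 | 0.560 |
| 0.60 | 0.619 | 0.636 | 0.653 |
| 0.70 | 0.716 | 0.729 | 0.742 |

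Example: 0.50^((24 − 2.71)/24) = 0.50^0.887 = 0.541, a shift of 4.1 points. At mid-window the shifts are 4.1, 3.6 and 2.9 points. Over the whole window they run from 1.6 points (S = 0.70, 45 days) to 6.0 points (S = 0.50, 120 days).

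**Step 3: comparison with sampling error.** The Wald half-width without censoring is 1.96 × √(S(1 − S)/38) = 0.159, 0.156 and 0.146 for S = 0.50, 0.60 and 0.70.

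**Step 4: what an analysis from transplant would estimate.** Simulation with n = 38, entry uniform on Days 45–120, constant hazard, 3,000 runs; estimates at 24 months after transplant.

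| S | Ordinary Kaplan-Meier (SD) | Delayed-entry Kaplan-Meier (SD) |
|---|---|---|
| 0.50 | 0.540 (0.080) | 0.523 (0.087) |
| 0.60 | 0.638 (0.077) | 0.623 (0.084) |
| 0.70 | 0.730 (0.071) | 0.716 (0.085) |

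Ordinary Kaplan-Meier matches the mid-window column of Step 2: the proportion of enrolled, treated patients alive at 24 months. Delayed entry sits close to the 45-day column: survival conditional on being alive at about the earliest entry. The two methods estimate different quantities, and neither is unconditional survival after transplant.

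**The case against.** **Loose wording.** Elsewhere in the same objectives the reference to transplant describes the setting and not a clock, as in the objective on immune effector cells. On that reading the OS objective would mean 2-year OS in a post-transplant population. This fails for OS: a time point is attached directly to the transplant, and the PFS objective beside it names its own, different origin.

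**Consequence.** The analysis sections agree on first dose, so a programmer would produce one unambiguous and valid number. OS is secondary, drives no sample size or decision, and the shift is small beside the CI. All of this stands. It limits the importance of the point, but the planned estimate still does not answer the stated objective.

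**Inputs.** n = 38 is a maximum. The SAP's efficacy-endpoint table assigns OS to the Efficacy Evaluable population while SAP 1.2 speaks of all enrolled patients, so fewer may be analysed. OS is also reported for patients at the MTD; at n = 20 the half-width is about 20–22 points. In the other direction, Protocol 7.1 allows consent up to 28 days before treatment. If enrolment is dated at consent, the gap could reach 120 + 28 = 148 days, putting the planned landmark at 28.9 months. The 2–6 point range is therefore illustrative, not a bound.

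**Delayed entry.** For at most 38 patients this may be more than a descriptive endpoint needs. It assumes that entry time is unrelated to survival, which is doubtful when late entry may reflect slow recovery. The early risk set is also small: in a further 6,000 simulated datasets per scenario, 0.1–0.3% of curves dropped to zero after an early death with one patient at risk. This is a fair caution; delayed entry is an option, not part of the core correction.

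**Conclusion.** The concern holds. The OS objective and the OS definition use different time origins in both documents, no text reconciles them, and carrying out the plan exactly would not estimate the stated objective. The conflict itself depends on no assumption.

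Only its size does. With a constant hazard, first dose at enrolment and 2-year OS of 50–70% from Day 1, the planned figure would understate survival at 24 months after transplant in the same patients by roughly 2–6 points. That is less than half of the 95% CI half-width at n = 38.

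The primary safety and MTD objectives are unaffected, and the Day 1 estimate is valid under its own label. The documents do not show which origin was intended. The point should be corrected before analysis, but it does not threaten the trial.

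**What to change.** Settle the OS origin before analysis.

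- **Simplest.** Reword the OS objective in the Protocol Synopsis, Protocol 2.2 and SAP 1.1 so that the 2 years run from the start of maintenance, matching PFS and the existing OS definition. The analysis does not change.
- **If survival 2 years after transplant is wanted.** Add an analysis from the transplant date, and keep the Day 1 estimate as a separately labelled result. Either use ordinary Kaplan-Meier, reported as the proportion of enrolled and treated patients alive at 24 months after transplant; or use delayed-entry Kaplan-Meier, reported as survival conditional on being alive near Day 45, with its independence assumption stated.

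In the same edit, correct the *or*/*to* slip in Protocol 10.4.2. Also align the OS definitions, which count deaths on study, with the SAP's OS event table, which also counts deaths during follow-up.

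**Cost.** One line of objective wording where it appears, with the protocol change going through the amendment process in Protocol 13.1, or one added analysis. No new data are needed: Protocol 7.2 already collects "Date of transplant", and 24 months after transplant falls earlier than the planned 2-year landmark. Delayed entry costs some precision (simulated SD 0.084–0.087 against 0.071–0.080) and can be unstable early on the curve.
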